Time to Progression Free Survival (PFS) is defined as the time from the first dose of the study drug to documented disease progression or death due to any cause. For Patients who neither progress nor die, the duration of response is censored on the last date the patient is known to be radiologically progression free.

Both the treatment groups are collectively used to represent the Overall group.

Patients qualifying in Intent-to-Treat (ITT) and Per-Protocol (PP) analysis sets are identical.

Program: xx.sas Figure Generation: ddmmmyyyy hh:mm:ss

<Note to Programmer>

[figure not shown]
Document Date: 12MAY2023.

In the first page plot will be by treatment groups and next page by overall.

Use same format for

1. Figure 14.2.3.5 Kaplan-Meier plot for PFS – Per Protocol Analysis

Protocol RP6530-2101 Figure 14.2.2.4 Best Response (% change from Baseline) in sum of lesion diameters plot ITT Analysis Set Page xx of yy

The Best Overall Response (BOR) is defined as the best visit response recorded from the start of the treatment until disease progression/recurrence.

Page 103 of 106 ST-AD-032 version 01

Document Date: 12MAY2023.

Best change from baseline represents the smallest value of change from baseline in sum of lesion diameter among all the visits. Patients with at least 1 post-baseline efficacy assessment are considered.

Patients qualifying in Intent-to-Treat (ITT) and Per-Protocol (PP) analysis sets are identical.

CR: Complete Response; PR: Partial Response; SD: Stable Disease; PD: Progressive Disease.

Use same format for

[figure not shown]
Document Date: 12MAY2023.

1. Figure 14.2.2.5 Best Response (% change from Baseline) in sum of lesion diameters plot – Per Protocol Analysis

Protocol RP6530-2101 Figure 14.2.2.6 Visit Wise Tumor Response Plot ITT Analysis Set

Document Date: 12MAY2023.

Page xx of yy

% Change from Baseline=((Sum of Lesions Diameter at Visit – Sum of Lesions Diameter at Screening)/Sum of Lesions Diameter at Screening)x100. Patients with at least 1 post-baseline efficacy assessment are considered.

Patients qualifying in Intent-to-Treat (ITT) and Per-Protocol (PP) analysis sets are identical.

<Note to Programmer>

In the first page plot will be by treatment groups and next page by overall.

Use same format for

Document Date: 12MAY2023.

1. Figure 14.2.2.7 Visit Wise Tumor Response Plot – Per Protocol Analysis

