5.2 Changes from the Analyses Planned in the Protocol

There were no changes in the analysis planned in the protocol of the study at the time of preparing this statistical analysis plan.

BASELINE, EFFICACY and Safety EVALUATIONS 6.

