6.4.1 Primary Efficacy Variable

The primary efficacy variable is the percentage of patients without disease progression at the end of 6 months i.e. 180 days:

Percentage = (patients without disease progression/total number of patients) *100.

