6.4.3 Additional Efficacy Variables

Duration of Treatment Exposure: Duration of treatment exposure is defined as the time from first dose to last dose of drug.

Duration of Response: Duration of response (DoR) is defined as the time from the first occurrence of partial or complete response to disease progression or death in patients who achieve complete or partial response. For patients who neither progress nor die, the duration of response will be censored on the last date the patient is known to be radiologically progression free.

Duration of clinical benefit: Duration of clinical benefit (DoCB) is defined as the time from the first dose of study drug to disease progression or death in patients who achieve complete response, partial response, or stable disease for 24 weeks or longer. For patients who neither progress nor die, the duration of response will be censored on the last date the patient is known to be radiologically progression free.

Proportion of patients with 6-Month and 1-year PFS.

PFS rate at 6-months or at 1-year: Proportion of patients who remained alive and progression-free at 6 months or at 1-Year

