7.3 Handling of Dropouts or Missing Data

Missing results/events will not be imputed. Imputations will be done for missing dates as follows.

Missing Dates for Adverse Events and Concomitant Medications

Adverse events and concomitant medications with completely or partially missing assessment dates will have imputation performed as explained below for the purposes of calculation of durations or relativity to study medication.

For the end of a concomitant medication or adverse event:

If only Day of end date is missing:

The last date of the month and year reported or the date of the final contact with the patient, whichever is earlier, will be used as the end date.

• If Day and Month of end date are missing:

The last date of year i.e. December 31 of the year reported or the date of the last study contact with the patient, whichever is earlier, will be used as the end date.

If Year of end date or complete end date is missing:

If the year of end of medication/event is missing or end date is completely missing, then no end date will be imputed.

For the start of a concomitant medication or adverse event:

• If only Day of start date is missing:

o If the start year and month of medication/event are the same as that for the first dose date, then following approach will be used:

CONFIDENTIAL Page 12 of 106

Document Date: 12MAY2023. ST-AD-032 version 01

- If the end date of medication/event is NOT before the first dose date or end date of medication/event is completely missing, then impute the start day as the day of first dose date
- Otherwise, impute the start day as 1.
- If the start year and month of medication/event are NOT same as that for the first dose date. then
 - Impute the start day as 1.

If Day and Month of start date are missing:

- If start year of medication/event is same as first dose year, then following approach will be used:
 - For medication, impute the start Month as January and the Day as 1 İ.
 - ii. For adverse event.
 - If the end date of event is NOT before the first dose date or end date of event is completely missing, then impute the start Month and Day as the Month and Day of first dose date;
 - Otherwise, impute the start Month as January and the Day as 1.
- If start year of medication/event is NOT same as first dose year, then
 - Impute start Month as January and the Day as 1.

If Year of start date or complete start date is missing:

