A patient with two or more prior non-drug treatments in the same system organ class (or with the same preferred term) is counted only once for that system organ class (or preferred term).

System organ classes are sorted in alphabetical order. Preferred terms are sorted within system organ class by descending order of frequency of overall preferred terms.

Prior non-drug treatments are those that were taken only prior to the first dose of study drug.

Reference Listing 16.2.x.x

Document Date: 12MAY2023.

Protocol RP6530-2101 Table 14.1.5.4 Summary of Concomitant Non-Drug Treatments Safety Analysis Set Page xx of yy

System Organ Class	Tenalisib 800 mg BID	Tenalisib 1200 mg BID	Overall
Preferred Term	(N=XX)	(N=XX)	(N=XX)
	n (%)	n (%)	n (%)
Patients with at least one Concomitant	xx (xx.x)	xx (xx.x)	xx (xx.x)
Non-Drug Treatment			
SOC1	xx (xx.x)	xx (xx.x)	xx (xx.x)
PT1	xx (xx.x)	xx (xx.x)	xx (xx.x)
PT2	xx (xx.x)	xx (xx.x)	xx (xx.x)
Etc.			

Percentages are based on the total number of patients (N) in each treatment group.

A patient with two or more concomitant non-drug treatments in the same system organ class (or with the same preferred term) is counted only once for that system organ class (or preferred term).

Non-drug treatments are coded using MedDRA (version 24.0).

System organ classes are sorted in alphabetical order. Preferred terms are sorted within system organ class by descending order of frequency of overall preferred terms.

Concomitant non-drug treatments are those that were taken while on study drug. The non-drug treatments that started after the discontinuation of study drug will also be termed as 'Concomitant non-drug treatments'

Reference Listing 16.2.x.x

Document Date: 12MAY2023.

Protocol RP6530-2101

Table 14.2.1.1

Summary of Patients Without Disease Progression at the End of 6 Months

ITT Analysis Set

	Tenalisib 800 mg BID	Tenalisib 1200 mg BID	Overall
	(N=xx)	(N=xx)	(N=xx)
Number (%) of patients without progression at the End of 6 months 95% CI*	xx (xx.x)	xx (xx.x)	xx (xx.x)
	(xx.x, xx.x)	(xx.x, xx.x)	(xx.x, xx.x)

The Intent - to - Treat (ITT) analysis set includes all patients who received at least 1 dose of study medication.

Percentages are based on the total number of patients (N) in each treatment group.

At 6 months, patients with treatment duration ≥180 days are summarized.

Reference Listing 16.2.x.x

Document Date: 12MAY2023

Program: xx.sas Table Generation: ddmmmyyyy hh:mm:ss

Use same format for

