- 1. Table 14.2.1.2 Summary of Patients without Disease Progression at the End of 6 Months by Type of Metastasis ITT Analysis Set <Column 1: same as table 14.2.1.1; Column 2: de novo metastasis; Column 3: recurrent metastasis; Column 4: Overall>
- 2. Table 14.2.1.3 Summary of Patients without Disease Progression at the End of 6 Months Per Protocol Analysis
- 3. Table 14.2.1.4 Summary of Patients with 6-Month and 1-Year Progression Free Survival ITT Analysis Set
 - <Column 1: First line "Number (%) of patients without Progressive disease/Death at 6 Month" Second line "Number (%) of patients without Progressive disease/Death at 1 year;

Add footnote-"At 1 year, patients with treatment duration ≥360 days are summarized."

- 4. Table 14.2.1.5 Summary of Patients with 6-Month and 1-Year Progression Free Survival by Type of Metastasis ITT Analysis Set
 - <Column 1: First line "Number (%) of patients without Progressive disease/Death at 6 Month"

 Second line "Number (%) of patients without Progressive disease/Death at 1 year;

Add footnote-"At 1 year, patients with treatment duration ≥360 days are summarized."

Column 2: de novo metastasis; Column 3: recurrent metastasis; Column 4: Overall>

5. Table 14.2.1.6 Summary of Patients with 6-Month and 1-Year Progression Free Survival – Per Protocol Analysis

^{*} The 95% CIs are reported using exact method based on binomial distribution.

Protocol RP6530-2101

Table 14.2.2.1

Summary of Objective Response Rate and Clinical Benefit Rate

ITT Analysis Set

	Tenalisib 800 mg BID	Tenalisib 1200 mg BID	Overall
	(N=xx)	(N=xx)	(N=xx)
Number (%) of patients			
95% CI*			
CR	xx (xx.x)	xx (xx.x)	xx (xx.x)
	(xx.x, xx.x)	(xx.x, xx.x)	(xx.x, xx.x)
PR	xx (xx.x)	xx (xx.x)	xx (xx.x)
	(xx.x, xx.x)	(xx.x, xx.x)	(xx.x, xx.x)
SD	xx (xx.x)	xx (xx.x)	xx (xx.x)
	(xx.x, xx.x)	(xx.x, xx.x)	(xx.x, xx.x)
SD>=24 weeks	xx (xx.x)	xx (xx.x)	xx (xx.x)
	(xx.x, xx.x)	(xx.x, xx.x)	(xx.x, xx.x)
PD	xx (xx.x)	xx (xx.x)	xx (xx.x)
	(xx.x, xx.x)	(xx.x, xx.x)	(xx.x, xx.x)
Not Evaluated	xx (xx.x)	xx (xx.x)	xx (xx.x)
	(xx.x, xx.x)	(xx.x, xx.x)	(xx.x, xx.x)
ORR (CR+PR)	xx (xx.x)	xx (xx.x)	xx (xx.x)
	(xx.x, xx.x)	(xx.x, xx.x)	(xx.x, xx.x)
CBR (CR+PR+SD>=24 weeks)	xx (xx.x)	xx (xx.x)	xx (xx.x)
,	(xx.x, xx.x)	(xx.x, xx.x)	(xx.x, xx.x)

The ITT analysis set includes all patients who received at least 1 dose of study medication. Percentages are based on the total number of patients (N) in each treatment group.

CONFIDENTIAL

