Page 42 of 106 ST-AD-032 version 01 Page xx of yy

* The 95% CIs are reported using exact method based on binomial distribution.

The BOR is defined as the best visit response recorded from the start of the treatment until disease progression/recurrence. The response rates (CR/ PR/ SD/SD>=24 weeks/PD) are estimated using (BOR) recorded in each patient. For the patients without any post-baseline efficacy assessment, BOR is considered as 'Not evaluated'.

For SD \geq 24 weeks, patients with treatment duration \geq 168 (\pm 7) days are summarized.

CR- Complete Response; PR- Partial Response; SD- Stable Disease; PD- Progressive Disease; ORR- Objective Response Rate; CBR- Clinical Benefit Rate. Reference Listing 16.2.x.x

Program: xx.sas Table Generation: ddmmmyyyy hh:mm:ss

Use same format for

Document Date: 12MAY2023.

1. Table 14.2.2.2 Summary of Objective Response Rate and Clinical Benefit Rate by type of metastasis – ITT Analysis Set <Column 1: same as table 14.2.2.1; Column 2: de novo metastasis; Column 3: recurrent metastasis; Column 4: Overall>

2. Table 14.2.2.3 Summary of Objective Response Rate and Clinical Benefit Rate – Per Protocol Analysis

CONFIDENTIAL Page 43 of 106 ST-AD-032 version 01

Protocol RP6530-2101 Table 14.2.3.1 Summary of Progression Free Survival ITT Analysis Set Page xx of yy

	Tenalisib 800 mg BID	Tenalisib 1200 mg BID	Overall
	(N=xx)	(N=xx)	(N=xx)
Number (%) of patients with Progressive Disease/Death	xx (xx.x)	xx (xx.x)	xx (xx.x)
Progressive Disease, n (%)	xx (xx.x)	xx (xx.x)	xx (xx.x)
Death, n (%)	xx (xx.x)	xx (xx.x)	xx (xx.x)
Number (%) of censored patients	xx (xx.x)	xx (xx.x)	xx (xx.x)
Reason for Censoring n(%)			
XXXXXXXXXXXXXX	xx (xx.x)	xx (xx.x)	xx (xx.x)
xxxxxxxxxxxxx	xx (xx.x)	xx (xx.x)	xx (xx.x)
Time to Progressive Disease/ Death (days)			
Quartiles (95% CI)*			
Q1	xx.x(xx.x, xx.x)	xx.x(xx.x, xx.x)	xx.x(xx.x, xx.x)
Median	xx.x(xx.x, xx.x)	xx.x(xx.x, xx.x)	xx.x(xx.x, xx.x)
Q3	xx.x (xx.x, xx.x)	xx.x (xx.x, xx.x)	xx.x (xx.x, xx.x)
Range (min, max)	(xx, xx)	(xx, xx)	(xx, xx)

The ITT analysis set includes data from all patients who received at least 1 dose of study medication.

Percentages are based on the total number of patients (N) in each treatment group.

CONFIDENTIAL

Page 44 of 106 ST-AD-032 version 01

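### Table-shell footnotes make time on drug a condition of the primary 6-month count and the 6-month and 1-year PFS counts, while the SAP text defines them by progression (and survival) status

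*SAP*

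**What the plan says.** The SAP text and the SAP shells give two rules for the same counts.

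- **Text, primary.** SAP 6.4.1: "The primary efficacy variable is the percentage of patients without disease progression at the end of 6 months i.e. 180 days". The formula there divides by the total number of patients. SAP 8.7.1 adds exact 95% limits and no exposure condition.
- **Text, PFS rates.** SAP 6.4.3: "Proportion of patients who remained alive and progression-free at 6 months or at 1-Year".
- **Shell, primary.** In SAP Section 12, Table 14.2.1.1 keeps a row label about being without progression and takes percentages on N per group, but its footnote reads "At 6 months, patients with treatment duration ≥180 days are summarized".
- **Shell, PFS rates.** Tables 14.2.1.2 to 14.2.1.6 are to use the same format, so they take over the 180-day footnote. Tables 14.2.1.4 and 14.2.1.5 have the row label "Number (%) of patients without Progressive disease/Death at 6 Month" (and the same for 1 year) and an added footnote: "At 1 year, patients with treatment duration ≥360 days are summarized". Table 14.2.1.6 has no footnote of its own. (These are the numbers in the shells. The list of outputs gives several of these tables the number 14.2.1.3.)
- **Treatment duration.** SAP 8.8.1 defines it as last day of dosing minus first day plus 1.
- **Missing data.** SAP 7.3: "Missing results/events will not be imputed". It then gives rules for missing dates only.

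The same device appears for stable disease of at least 24 weeks and for duration of clinical benefit (Table 14.2.2.1, Tables 14.2.4.4 to 14.2.4.6, Figure 14.1.6.2). There the footnote reads "24 weeks, patients with treatment duration" of at least 168 (±7) days. SAP 6.4.2, 6.4.3 and 8.7.2 define these by how long the disease stays stable.

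**The concern.** Exposure and disease status are different things in this trial. Protocol 4.3 lets a patient stop drug without progression, for toxicity, intercurrent illness, withdrawal of consent or non-compliance. SAP 5.1 records that the study was closed before all patients had progressed. A patient can therefore be progression-free at a landmark and have less than 180 or 360 days of treatment. No passage says which rule then governs.

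What is at stake is the reported primary rate and which patients stand behind it. As written, the text and the shell can give different numerators from the same data, and the choice would fall to programming, in an open-label study that had already closed.

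**Working it through.** **Inputs.** 20 patients per group and a planning rate of 20%, that is 4 of 20 (Protocol 9.2, SAP 4.5). Exact binomial 95% limits (SAP 8.7.1). Scans at C3D1 and about every 8 weeks, ±7 days (Protocol 8.1). Cycles of 28 days.

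**Check of the interval method on the plan's own figure.** Clopper-Pearson limits for x of n are the α/2 quantile of Beta(x, n−x+1) and the 1−α/2 quantile of Beta(x+1, n−x). For 4/20 at 90% they are 7.1% and 40.1%. The distance to the lower limit is 20.0 − 7.1 = 12.9, which matches the stated precision of 13%. (The half-width is 16.5%. That is a separate matter, and nothing here depends on it.)

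**Scan days.** Day = 1 + (c − 1) × 28:

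- C7D1 = 169 (window 162–176), C9D1 = 225 (218–232)
- C13D1 = 337 (330–344), C15D1 = 393 (386–400)

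No scheduled window contains day 180 or day 360. A patient still dosed on day 180 and one who stopped on day 178 can both have day 169 as their last scheduled scan.

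**The rules side by side**, for assumed patients:

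| Patient | 6.4.1 read literally | 6.4.3 PFS rate | Shell: row label plus footnote |
|---|---|---|---|
| A. Clean scan day 169, last dose day 178 for toxicity, no progression or death by day 180 | success | success | non-success (178 − 1 + 1 = 178 < 180) |
| B. Drops out after a clean C3D1 scan | success, as no progression is recorded | text gives no rule | non-success |
| C. Dies on day 100 without progression | success | failure | non-success |
| D. Progression-free, dosing ended before day 360 by study closure | not affected at day 180 if treated that long | 1-year status not established; text gives no rule | 1-year non-success |
| E. Progression-free and on drug beyond day 180 | success | success | success |

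The footnote contradicts both text definitions for A. For B and D it settles, without saying so, a question that the text leaves open. For C it gives the same answer as 6.4.3, but not the answer of 6.4.1 read literally.

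**Size per patient.** One patient is 1/20 = 5 points in a group and 1/40 = 2.5 points in the Overall column.

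- Group: 4/20 = 20% (exact 95% CI 5.7–43.7) against 3/20 = 15% (3.2–37.9).
- Overall: 8/40 = 20% (9.1–35.6) against 7/40 = 17.5% (7.3–32.8).

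**Range.** The documents do not say how many patients are like A. Assume that 4 of 20 meet the shell rule and that k more are progression-free at day 180 but off drug. The status-based count is then:

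| k | Count | Rate | Exact 95% CI |
|---|---|---|---|
| 0 | 4/20 | 20% | 5.7–43.7 |
| 1 | 5/20 | 25% | 8.7–49.1 |
| 2 | 6/20 | 30% | 11.9–54.3 |
| 3 | 7/20 | 35% | 15.4–59.2 |
| 4 | 8/20 | 40% | 19.1–63.9 |

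**What Kaplan-Meier adds.** Assume progression in 8, 5 and 3 patients on days 57, 113 and 169, one patient censored at a clean scan on day 113, and 3 progression-free beyond day 180. The estimate at day 180 is (12/20)(7/12)(3/6) = 17.5% (log-log 95% CI 4.5–37.4), against a crude 3/20 = 15%. The gain comes from the censored patient's partial follow-up.

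**24-week cut.** 24 × 7 = 168 days. With ±7 attached to a lower bound, the cut can be read as day 161, 168 or 175.

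**The case against.** The best defence is that the footnote is an operational convention and a cautious one. It keeps early dropouts and deaths without progression out of the successes, where 6.4.1 read literally would put them. Time on drug also says something about the tumour, because confirmed progression ends treatment (Protocol 4.3) and scans are done when progression is suspected (Protocol 8.1). Protocol 9.1 leaves derivation details to the SAP, and Section 12 is part of the SAP. The Kaplan-Meier analysis of PFS is planned in 8.7.2 with its own censoring rule. Listings 16.2.6.4, 16.2.6.6 and 16.2.1.4 would let a reader recount 20 patients per group.

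Much of this stands, and it limits the point. It does not remove it: no SAP text states the footnote as a missing-data rule, and a rule that fixes the primary numerator belongs in the endpoint definition.

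Several stronger readings are tempting and not supported:

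- *Duration replaces status, so a progressed patient still on drug counts as a success.* The row labels still require absence of progression. Status plus duration is the natural reading.
- *The 180-day cut carries no tumour information.* It brings no scheduled scan, but being on drug is not uninformative, for the reasons above.
- *The SAP conceals a change.* SAP 5.2 says "There were no changes in the analysis planned in the protocol of the study", but given Protocol 9.1 an operational rule in a shell is not plainly a changed analysis.
- *The higher dose is penalised through more toxicity stops.* The documents give no stopping rates by dose.
- *Every dropout or death that the footnote removes is an error.* Those patients differ only from a literal reading of 6.4.1, and other reasonable rules would also score them as non-successes.

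**Conclusion.** The concern holds as a conflict between the SAP text and its shells on how the primary count and the crude PFS rates are derived. Under the natural reading, a patient who is progression-free but off drug before the landmark is scored as a non-success, which 6.4.1 and 6.4.3 do not require. The 1-year count is especially exposed because of the early closure.

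The effect is 5 points per patient in a group of 20. It rests on at least one patient being in that position, and the true number may be zero. No success threshold or test is planned, so no formal decision changes. No bias between the doses is claimed. The planned Kaplan-Meier analysis is not contradicted. The 168 (±7) cut is a smaller drafting point on secondary outputs. This should be fixed before the tables are produced, but it does not undermine the trial.

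**What to change.** 1. In Tables 14.2.1.1 to 14.2.1.6, remove treatment duration as the criterion for success. Keep that count at most as a labelled sensitivity analysis.
2. Derive status at days 180 and 360 from documented progression dates and, for the PFS rates, from the death dates already collected. Show patients whose status at the landmark is not established in a separate row. State one rule in 6.4.1 and 6.4.3 for how those patients, and deaths without progression, are counted. The documents set neither a minimum scan date nor death as a failure of the primary variable, so these are choices for the sponsor to make and state.
3. Tabulate Kaplan-Meier estimates with 95% CIs at days 180 and 360 from the PFS analysis already planned in 8.7.2, and note that they assume non-informative censoring.
4. For stable disease of at least 24 weeks and duration of clinical benefit, use dated assessments. If the duration proxy stays, state it in 6.4.2 and 6.4.3 with a single cut-off.

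The cost is SAP and shell wording plus minor programming, with no new data. The crude count still cannot recover a patient's status after the last scan. The Kaplan-Meier assumption may fail for patients who stop because of toxicity.

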8.7.2 Analysis of Secondary Efficacy Variables

These secondary efficacy variables will be analysed and summarised to evaluate safety and tolerability of tenalisib.

• Overall Response Rate (ORR): It is defined as sum of CR and PR rates.

The percentages of CR+PR will be calculated and presented along with 95% confidence intervals of these percentages.

This data will be summarized using frequency, and percentage along with 95% confidence intervals of these percentages using exact method based on binomial distribution.

The corresponding listing will also be provided.

• Clinical Benefit Rate (CBR): It is defined as sum of CR, PR and SD at 24 weeks or longer.

The percentages of CR+PR+SD>=24 weeks will be calculated and presented along with 95% confidence intervals of these percentages.

This data will be summarized using frequency, and percentage along with 95% confidence intervals of these percentages using exact method based on binomial distribution.

The corresponding listing will also be provided.

Progression Free Survival (PFS): It is defined as time from the first dose of study drug to
documented disease progression or death due to any cause.
 PFS is measured from the time of first dose of study drug to radiographic (or tumour marker as
applicable) documentation of disease progression or death due to any cause. Patients who did not
progress or die will be censored on the last date the patient is known to be radiologically
progression free. The summary table for PFS rate at 6-Month and 1-year by metastasis type will
also be provided.

This variable will be analyzed via Kaplan-Meier methodology and displayed graphically for each treatment group and overall. The following reports will be generated:

- The Q1, median and Q3 PFS time will be provided. The 95% CI for the Q1, median, and Q3 PFS time will be presented for each treatment group and metastasis group using Brookmeyer-Crowley method.
- The number and % of patients with disease progressive events (further divided into progression or death) will be provided.
- The number and % of patients censored (further divided by reasons for censoring) will be provided.
- Kaplan-Meier curves will be produced.
- · A listing of PFS data will be provided.

Additional efficacy variables

Duration of Treatment: Duration of treatment is defined as the time from first dose to last dose of drug.

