Time to Progression Free Survival (PFS) is defined as the time from the first dose of the study drug to documented disease progression or death due to any cause. For Patients who neither progress nor die, the duration of response is censored on the last date the patient is known to be radiologically progression free.

*Quartiles are calculated using Kaplan-Meier Estimate method. The 95% confidence intervals are calculated using Brookmeyer and Crowley Method.

Reference Listing 16.2.x.x

Document Date: 12MAY2023.

Program: xx.sas Table Generation: ddmmmyyyy hh:mm:ss

Use same format for

1. Table 14.2.3.2 Summary of Progression Free Survival by type of metastasis – ITT Analysis Set <Column 1: same as table 14.2.3.1; Column 2: de novo metastasis; Column 3: recurrent metastasis; Column 4: Overall>

2. Table 14.2.3.3 Summary of Progression Free Survival- Per Protocol Analysis

Protocol RP6530-2101 Table 14.2.4.1 Summary of Duration of Response ITT Analysis Set

Document Date: 12MAY2023.

Page xx of yy

	Tenalisib 800 mg BID (N=xx)	Tenalisib 1200 mg BID (N=xx)	Overall (N=xx)
N 1 (0/) CD 4 (1/1 D 4/1/C 1/4	. ,		
Number (%) of Patients with Partial/Complete Response *	xx.x (xx.x)	xx.x (xx.x)	xx.x (xx.x)
Number (%) of Censored Patients	xx.x (xx.x)	xx.x (xx.x)	xx.x (xx.x)
Reason for Censoring n (%)			
xxxxxxxxxxxxxx	xx.x (xx.x)	xx.x (xx.x)	xx.x (xx.x)
Duration of Response (days)			
Quartiles (95% CI)*			
Q1	xx.x(xx.x, xx.x)	xx.x(xx.x, xx.x)	xx.x(xx.x, xx.x)
Median	xx.x(xx.x, xx.x)	xx.x(xx.x, xx.x)	xx.x(xx.x, xx.x)
Q3	xx.x(xx.x, xx.x)	xx.x (xx.x, xx.x)	xx.x (xx.x, xx.x)
Range (min, max)	(xx,xx)	(xx,xx)	(xx,xx)

The ITT is the primary analysis population and will include data from patients who have received at least 1 dose of study medication.

Percentages are based on the total number of patients with Partial/Complete Response in each treatment group.

Duration of Response (DoR) is defined as time from the first occurrence of partial or complete response to disease progression or death in patients who achieve complete or partial response. For patients who neither progress nor die, the duration of response is censored on the last date the patient is known to be radiologically progression free.

CONFIDENTIAL

Page 46 of 106 ST-AD-032 version 01

^{*}Percentages are based on the total number of patients (N) in each treatment group.

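### The 1-year PFS rate in SAP Tables 14.2.1.4 to 14.2.1.6 scores a patient who was event-free at early closure with under 360 days of dosing as not progression-free, although SAP 8.7.2 censors that patient

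*SAP*

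**What the plan says.** **Definition.** SAP 6.4.3 gives the 6-month and 1-year PFS rates as "Proportion of patients who remained alive and progression-free at 6 months or at 1-Year". It sets no dosing condition and no rule for a patient followed for less than a year.

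**Shells (SAP Section 12).** Tables 14.2.1.4 to 14.2.1.6 reuse the layout of Table 14.2.1.1. (The output index numbers them all 14.2.1.3; the shell numbers are used here.) The 1-year row is labelled "Number (%) of patients without Progressive disease/Death at 1 year", and Tables 14.2.1.4 and 14.2.1.5 add the footnote "At 1 year, patients with treatment duration ≥360 days are summarized". The shared layout brings "At 6 months, patients with treatment duration ≥180 days are summarized" for 6 months, an exact binomial 95% CI, and the denominator rule "Percentages are based on the total number of patients (N) in each treatment group". That rule overrides the SAP 7.1 default of non-missing assessments. Table 14.2.1.6 has no footnote of its own and inherits the rule only through the layout. There is no row for patients censored or not yet at 1 year.

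**PFS analysis.** Under SAP 8.7.2, patients who did not "progress or die will be censored on the last date the patient is known to be radiologically" progression-free. The same item announces the landmark table: "The summary table for PFS rate at 6-Month and 1-year by metastasis type will" be provided. The PFS shell, Table 14.2.3.1, gives event and censoring counts, quartiles and a range; its footnote reads "Quartiles are calculated using Kaplan-Meier Estimate method". It has no landmark rate.

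**Closure.** SAP 5.1 reports that the study closed early, before all patients had progressed. SAP 5.2 reports no change to the analyses.

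**The concern.** The row label promises a statement about progression and death, but the counting rule is about length of dosing. For patients taken off drug because the study ended, the two come apart. Closure is not treatment failure, yet such a patient leaves the numerator and stays in the denominator.

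The 1-year figure would then depend partly on how long before closure a patient started. It could also sit below the Kaplan-Meier curve at Day 360 in the same report, with nothing in the table to explain the gap. Because the PFS table gives quartiles only, the crude count is the only tabulated 1-year rate.

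**Working it through.** The plan gives no figure for the 1-year rate, so there is none to reproduce. The 13% precision in SAP 4.5 concerns the 6-month percentage and does not enter here. Inputs from the documents: 20 patients per group and 20% progression-free at 6 months (SAP 4.5); Day 180 and Day 360 thresholds (shells); scans at C3D1 and about every 8 weeks (Protocol 8.1); eCRF 1.0 dated 24 Sep 2021 (SAP 2); SAP dated 12 May 2023.

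**1. One patient.** Take a patient event-free at closure after 300 days of dosing. Shell: 300 < 360, so not in the numerator but in N. SAP 8.7.2: censored at the last progression-free scan. SAP 6.4.3: no rule. A patient already dosed for 360 days or more at closure counts as a success.

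**2. Per-patient size.** 1/20 = 5 points in an arm and 1/40 = 2.5 points in the Overall column. This is a maximum, since the patient might have progressed before Day 360 anyway.

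**3. Illustration (assumed data).** N = 20, 16 events before Day 300, 4 patients event-free. Let closure cut off 0, 1, 2, 3 or 4 of the four at Day 300. The shell gives 20%, 15%, 10%, 5% or 0%, and its exact 95% CI moves from 5.7–43.7% to 0–16.8%. The Kaplan-Meier estimate at Day 360 is 20% each time, because all events precede the censoring.

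**4. Expected rate.** Let f be the share of patients with under 360 days of potential follow-up. With no dropout, expected shell rate = S(360) × (1 − f).

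| S(360) | f = 0 | 10% | 20% | 40% |
|---|---|---|---|---|
| 4% (0.20² = 0.04: planned 6-month rate, constant hazard) | 4.0% | 3.6% | 3.2% | 2.4% |
| 25% (assumed) | 25% | 22.5% | 20% | 15% |

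**5. What the dates allow for f.** From 24 Sep 2021 to 12 May 2023 is 595 days. The SAP describes closure in the past tense, so 360 days of dosing by then needs a first dose by 18 May 2022, which is 236 days after eCRF 1.0. If dosing did not start before eCRF 1.0 (assumed), f is zero only if everyone started within those 236 days. Uniform accrual over 300 days (assumed) would give f = (300 − 236)/300 = 21%. Neither enrolment nor closure dates are given.

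**6. Simulation.** n = 20 per arm, 4,000 replicates, exponential PFS, true 1-year rate 25% (assumed), uniform accrual, no dropout. The scan columns detect progression on Days 57, 113, … and censor at the last scan.

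| Accrual / closure (days) | f | Shell | Kaplan-Meier | Shell, scans | Kaplan-Meier, scans |
|---|---|---|---|---|---|
| 145 / 505 | 0 | 25.0% | 25.0% | 27.2% | 27.2% |
| 180 / 505 | 0.19 | 20.4% | 25.3% | 22.0% | 27.3% |
| 300 / 596 | 0.21 | 19.9% | 25.3% | 21.4% | 27.1% |
| 240 / 500 | 0.42 | 14.6% | 25.0% | 15.9% | 27.2% |

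The excess over 25% in the scan columns is timing: the last scan before Day 360 falls on Day 337, and 0.25^(337/360) = 0.273. It is present in both methods at f = 0.

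**7. Six months.** With no dropout (240 / 500) there is no gap: 20.0% for both. With 10% dropout (assumed) and scans, the shell gives 19.8% and Kaplan-Meier 22.1% for a true 20%, so there the crude figure is the nearer one.

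**The case against.** **No breach of a Kaplan-Meier rule.** A reader might infer that the SAP breaks its own method. It does not. SAP 6.4.3 describes a proportion, and in SAP 8.7.2 the variable analysed by Kaplan-Meier is PFS time; nothing says the landmark rate is a Kaplan-Meier estimate. Counting unobserved patients as failures is a known conservative convention. This stands, and it limits the point to an inconsistency. The convention is not stated, however, and the row label says something else.

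**Not every patient event-free at closure.** A reader might also infer that all such patients are scored as failures. Only those with under 360 days of dosing are. The disposition shell runs to Cycle 15 and the response listing to C19D1, so some patients were expected to pass a year.

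**No affected patient can be shown.** True. Every non-zero f above is assumed, and at the planned rate the effect is trivial. The 25% has no source in the documents, and an exact 95% CI for 5/20 is 8.7–49.1%, far wider than these shifts.

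**The crude figure can have smaller error.** With 8-weekly scans and a true 25%, root-mean-square error (shell vs Kaplan-Meier) is 0.096 vs 0.101 at f = 0.19 and 0.099 vs 0.105 at f = 0.21; only at f = 0.42 does the order reverse (0.121 vs 0.111). In bias, the crude figure is nearer the truth while 27.3% × (1 − f) exceeds 22.7%, that is for f below about 17%. The numbers stand, but they show two biases offsetting: an upward one from scan timing, which full follow-up shares, and a downward one from closure. That is no defence of the rule.

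**The report will show the curve anyway.** The Kaplan-Meier plot, censoring counts and PFS listing are planned, so a careful reader could recover the estimate. That softens the consequence but leaves the only tabulated figure unexplained. Protocol 1.6 also allows progression information to be collected at a remote end-of-study contact, but the shell rule uses dosing time and would ignore it.

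**Conclusion.** The point holds as an inconsistency between shell and text. For the 1-year line, Tables 14.2.1.4 to 14.2.1.6 count an event-free patient with under 360 days of dosing at closure as not progression-free; SAP 6.4.3 sets no dosing condition and SAP 8.7.2 censors that patient. The error from closure is downward only, up to 5 points per affected patient in an arm of 20. The number affected is unknown and may be zero. At the planned 6-month rate with constant hazard, a share of 20% moves the expected 1-year rate from 4.0% to 3.2%; larger gaps need both a higher true rate and a substantial share, and both would be assumptions.

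A reader might go further and conclude that the dose comparison is distorted. The documents do not support that: patients are randomised in parallel, so closure should act on both arms alike on average, and these are additional, descriptive variables with no planned test. Nor does the point extend to the 6-month line, where closure produced no gap in the scenario checked. It is worth correcting before the tables are produced, but it does not threaten the trial's main conclusions.

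**What to change.** For the 1-year line only, in SAP 6.4.3, SAP 8.7.2 and the shells for Tables 14.2.1.4 to 14.2.1.6:

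- Report the Kaplan-Meier estimate at Day 360 from the planned PFS analysis, with its 95% CI, the number at risk and the number censored before Day 360.
- Keep the treatment-duration proportion beside it as a labelled conservative sensitivity figure. Add a footnote saying that patients not followed to Day 360 are counted as not progression-free, and how many there are.
- Leave the 6-month line consistent with primary Table 14.2.1.1, so that the report does not carry 6-month figures from two methods.

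The cost is SAP wording and three shells; the estimate comes from survival output already planned, and no new data are needed. The downsides should be stated. Few patients may be at risk at 1 year (about 0.4 to 5 of 20 per arm across the scenarios run, with and without 10% dropout). Kaplan-Meier assumes non-informative censoring, which stops for toxicity may violate. With 8-weekly scans any Day 360 estimate sits slightly high (about 27% for a true 25%). If nobody is censored before Day 360, the two figures agree and nothing is lost.
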